## 1.0 INTRODUCTION

Title	Pulmonary Functional Imaging for Radiation Treatment Planning for Lung Cancer
Short Title	SPECT/CT for Radiation in Lung Cancer
Phase	Pilot Study
Methodology	Single Arm Open-Label
Study Duration	2 years
Study Center(s)	University of Washington Medical Center
Objectives	To utilize SPECT/CT imaging with 99mTc-MAA and 99mTc-DTPA to accurately identify functional lung in patients receiving radiation treatment for lung cancer, and characterize tissue response to radiation. The long-term goal being to use functional imaging to guide radiation treatment planning, so functional lung tissue can be preferentially avoided, which will reduce radiation induced pulmonary toxicity allowing for increased dose delivery to the primary tumor.
Number of Subjects	20 evaluable subjects
Diagnosis and Main Inclusion Criteria	Patients diagnosed with non-metastatic lung cancers receiving radiation treatment, with impaired pulmonary function
Study Product, Dose, Route, Regimen	99mTc-MAA and 99mTc-DTPA SPECT/CT scans
Duration of administration	Drug administration will consist of 3 SPECT/CT scans with 99mTc-MAA and 99mTc-DTPA (one baseline scan which is standard of care, two follow up scans which are experimental and paid for by departmental research funds). The two experimental scans will be at mid-radiation treatment and approximately 3 months post-treatment.
Statistical Methodology	Outside the radiation field, normal lung tissue ventilation and perfusion over serial imaging will be assessed for stability using regression analysis, Pearson correlation, and Dice coefficient. Inside the radiation field, dose response curves will be developed for radiation dose versus changes in ventilation and perfusion. Gradient search algorithm in MIM 6.0. will be used to identify perfused and ventilated lung.

This document is a protocol for a human research study. This study is to be conducted according to US and international regulations, applicable government regulations and Institutional research policies and procedures.

## 2.0 BACKGROUND

### 2.1 Study Disease

Lung cancer is the most common cause of cancer related mortality in the US. Radiation therapy is a main treatment modality for lung cancer: for resectable tumors, radiation can be given pre-operatively or post-operatively to improve local tumor control and outcomes; for unresectable tumors, radiation can be given as definitive treatment for the cancer, either alone or in combination with chemotherapy.

Local recurrence remains a main cause of treatment failure in lung cancer. For stage III lung cancer treated with definitive chemoradiation, local failure rates range from 30% to 50% [1, 2]. Escalating radiation dose is one approach that may improve local control [3-5]. However, this approach has seen little success in recent dose escalation trials [6]. One potential limitation to radiation dose escalation is radiation induced toxicity. In the thoracic region, pulmonary toxicity is one major source of dose limitation. Many lung cancer patients are smokers and have poor baseline pulmonary function secondary to pulmonary co-morbidities, such as COPD. Moderate to severe radiation induced pulmonary toxicity occurs in 10-20% of patients receiving definitive treatment to a therapeutic dose of 60Gy and is fatal in 2-3% of these patients.[7]

Due to the prevalence of tobacco use in the lung cancer population, a significant percentage of patients have underlying parenchymal lung disease, which frequently has heterogeneous involvement. Differences in perfusion and ventilation leads to regional variations in pulmonary function. Perfusion imaging is an established technique to identify functional and non-functional zones within normal lung and is routinely used to predict post-operative pulmonary function in patients planned for pulmonary resection [8]. Current radiation treatment planning treats the lung as a homogeneously functioning organ and does not take regional variances in pulmonary function into account. Recent advances in radiation treatment planning and delivery, such as 3-D conformal radiation therapy and intensity modulated radiotherapy allow for preferential sparing of anatomic substructures in close proximity to the primary tumor. Other radiation treatment modalities, such as proton radiation therapy, provide greater ability to carefully choose radiation beam path, to selectively avoid lung regions.

## **2.2 Rationale for Use of SPECT/CT 99mTc-MAA and 99mTc-DTPA Scans**

SPECT imaging is a sensitive method of detecting regional lung function such as ventilation and perfusion. Radiation has been shown to affect both lung ventilation and perfusion. Data from Duke University and NKI using SPECT imaging have suggested a dose-response relationship between decrease in lung ventilation and perfusion and radiation dose delivered [9]. With more advanced imaging methods and the addition of CT scan to SPECT imaging, it is possible to improve contrast resolution relative to planar scintigraphy, and quantitative accuracy from attenuation correction [10, 11]. By integrating SPECT/CT scans into the radiation planning process, it is also possible to obtain scans in the radiation treatment position, allowing for more accurate calculation of radiation dose and functional image intensity at the voxel scale, leading to more precise dose-response characterization.

## **2.3 Clinical Data to Date**

SPECT/CT 99mTc-MAA and 99mTc-DTPA scans are both in use clinically for evaluating lung perfusion and ventilation, respectively. A landmark study showed that intravenous 99mTc macroaggregates were shown to accurately predict functional loss (FEV 1) 3 months postpneumonectomy [12]. Radionuclide-labeled tracers for perfusion scanning remains the gold standard for predicting postoperative lung function [13]. The radiation oncology community has not adopted the use of functional imaging to aid in radiation planning. The standard of care in radiation oncology is to treat all lung tissue as identical when calculating radiation dose and probability of complications.

## **2.4 Risks/Benefits**

The only risk to patients in this study is the risk associated with the two additional SPECT/CT 99mTc-MAA and 99mTc-DTPA scans. The radiation treatment patients receive will be standard of care. Risks associated with the two SPECT/CT 99mTc-MAA and 99mTc-DTPA scans include: patient time; radiation dose from radioactive tracers and scans (~ 30 mSv per session, which is about 0.1% of the usual

radiation dose for lung cancer treatment, typically around 60 Gy), and intravenous injection and potential for bleeding, pain, infection, and injection site reaction. Please see consent form for further details on potential risks.

The benefit gained from this study is the knowledge of whether SPECT/CT  $^{99m}\text{Tc}$ -MAA and  $^{99m}\text{Tc}$ -DTPA scans can identify functional lung tissue that remains ventilated and perfused over time. If we are able to reliably identify functional lung tissue, we can preferentially protect those lung regions from radiation, which can decrease radiation induced lung injury. We will also learn about the effect of radiation on the spatial and temporal dynamics of lung ventilation and perfusion, which can better help us design radiation treatments to safely treat tumors while minimizing lung toxicity.

## 3.0 STUDY OBJECTIVES

### 3.1 Primary Objective

To utilize SPECT/CT imaging with  $^{99m}\text{Tc}$ -MAA and  $^{99m}\text{Tc}$ -DTPA to identify functional lung on serial imaging in patients receiving radiation treatment for lung cancer, as well as to characterize reproducibility of perfusion and ventilation in non-irradiated lung tissue.

Hypothesis: For lung tissue outside the radiation field, perfusion and ventilation as defined by SPECT/CT imaging with  $^{99m}\text{Tc}$ -MAA and  $^{99m}\text{Tc}$ -DTPA will exhibit smaller changes over time than tissue inside the radiation field. Compared to the pre-radiation scan, lung tissue receiving radiation dose below the 20th percentile of total lung will have perfusion and ventilation that remain constant or increase at the mid-radiation treatment scan and 3-months post-treatment scans. By contrast, lung tissue receiving radiation dose above the 80th percentile of total lung will have perfusion and ventilation that decrease at the mid-radiation treatment scans and 3-months post-treatment scans.

### 3.2 Secondary Objective

a) To estimate the dose response relationship on multiple spatial scales (global lung, regional lung, lung image voxel) between radiation dose and changes in lung ventilation and perfusion, both acutely (mid-radiation treatment) and long term (3 months post-treatment), using SPECT/CT imaging with  $^{99m}\text{Tc}$ -MAA and  $^{99m}\text{Tc}$ -DTPA.

Hypothesis: Compared to the current models of radiation dose response for lung tissue, using CT in addition to SPECT imaging acquired in the radiation treatment position, a more accurate regional dose response relationship between radiation dose and changes in lung function can be generated with superior volumetric and quantitative data.

b) To estimate the degree of radiation response in lung tissue with varying levels of function (i.e. compare radiation dose response of well ventilated and well perfused tissue against lung tissue with poor perfusion and ventilation). This may establish a threshold of lung tissue that would be “safe” to treat without significantly affecting lung function.

Hypothesis: Well-perfused and ventilated lung tissue has a different radiation dose response curve than lung tissue that receives poor ventilation and perfusion (upper quartile versus lower quartile of perfused and ventilated tissue image intensity distributions). The dose-response relationship can be modeled either as a linear or sigmoid function.

### 3.3 Exploratory Objective

To evaluate proton radiation therapy for functional lung sparing in lung cancer through treatment planning comparisons to conventional photon radiation therapy.

Hypothesis: Unique physical characteristics of proton radiation allow for fewer external radiation beam pathways through normal tissue to achieve similar tumor dose coverage with photon radiation, leading to superior functional lung sparing.

## 4.0 STUDY DESIGN

### 4.1 General Design

This is a pilot study of utilizing SPECT/CT imaging with  $^{99m}\text{Tc}$ -MAA and  $^{99m}\text{Tc}$ -DTPA to accurately identify functional lung tissue on serial imaging in patients receiving radiation treatment for lung cancer. The long-term goal being to use functional imaging to help with radiation planning, which can preferentially spare functional lung tissue, leading to reduced pulmonary toxicity. Conversely, this has the potential for allowing increased radiation dose to the tumor while keeping normal tissue dose the same as conventional photon radiation therapy.

Patients will have a total of 3 SPECT/CT imaging with  $^{99m}\text{Tc}$ -MAA and  $^{99m}\text{Tc}$ -DTPA. The first scan will be routine medical care (not experimental) and will take place prior to initiation of radiation treatment. Two follow up scans will be part of the protocol, one at mid-radiation treatment, and one about 3 months post-radiation treatment.

### 4.2 Endpoints

#### 4.2.1 Primary Endpoint

In this study, patients with lung cancer will undergo SPECT/CT imaging with  $^{99m}\text{Tc}$ -MAA and  $^{99m}\text{Tc}$ -DTPA at the time of radiation treatment planning. All image datasets will be imported into MIM 6.0, and fused with the radiation treatment planning CT and radiation plan. Lung tissue will be divided into tissue outside the radiation field (dose < 20th percentile of total lung dose) and tissue inside the radiation field (dose > 80th percentile of total lung dose). This process will be repeated for the mid-treatment scan and 3 months post-treatment scan. Lung tissue outside the radiation field will be compared on serial scans and their perfusion and ventilation quantified. There should be insignificant changes in perfusion and ventilation in >80% of lung tissue outside the radiation field. Lung tissue inside the radiation field will also be compared, and should yield significant differences in ventilation and perfusion between pre, mid, and post-treatment scans.

We will analyze the perfusion and ventilation data through multiple methods. Image sets from all 3 time points (before radiation, mid-radiation, 3-months post-radiation) will be fused using rigid registration. Regions of interest within the lung will be defined using automated and semi-automated methods, including simple thresholds and gradient-search algorithms. For each tracer, uptake value will be calculated for each voxel. For lung tissue outside the radiation field, summary statistics such as total regional uptake and mean regional uptake by lobe will be compared across the time points using parametric and non-parametric statistical testing. Voxel-based correlation, including Pearson linear and Spearman rank, will be performed to measure the stability of uptake between time points. Lastly, metrics of ventilation and perfusion volume overlap between time points will be estimated using the Dice coefficient.

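### The 'inside the field' label is always the top fifth of lung by dose, so it does not track the field: small fields dilute the primary contrast and the dose-response curves inherit the label

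*Combined protocol and SAP*

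**What the plan says.** Section 4.2.1 (Primary Endpoint) sets the lower cut: "Lung tissue will be divided into tissue outside the radiation field (dose < 20", completed there as a 20th percentile. The upper cut follows in the same sentence: "percentile of total lung dose) and tissue inside the radiation field", the latter set as dose above the 80th percentile. The hypothesis in 3.1 has the same structure. Tissue below the 20th "percentile of total lung will have perfusion and ventilation that remain constant or increase", and tissue above the 80th "percentile of total lung will have perfusion and ventilation that decrease".

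The low-dose region stands in for unirradiated lung, since 3.1 also aims "to characterize reproducibility of perfusion and ventilation in non-irradiated lung tissue". Section 4.2.1 repeats the division for the mid-treatment and post-treatment scans.

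No section defines the field by a dose in Gy, an isodose line, a beam edge or a share of the prescription. Total lung is not defined either. The nearest text on regions is "Regions of interest within the lung will be defined using automated and semi-automated methods", which names thresholds and gradient search but does not mention tumour or target volume. Section 4.2.2 restricts the dose-response curves to tissue carrying the 'inside' label.

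Sections 5.1.2 and 5.1.3 admit all stages planned for at least 45 Gy, including post-operative patients and those without measurable disease.

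**The concern.** A percentile cut fixes the volume of each region and lets its dose float. The names given to the regions suggest the reverse, that membership depends on whether the tissue was irradiated. With eligibility this broad, the share of lung in the field can differ widely among 20 patients while the 'inside' share stays at one fifth.

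Where the field is small, the top fifth by dose is made up with lung that received little dose. The primary hypothesis expects function to fall inside and to hold or rise outside, so mixing off-field lung into 'inside' shrinks the difference being sought. A weak or null contrast could then mean that radiation had little effect, or that the region was mostly not in the field, and the plan reports nothing that would separate the two. The secondary curves, drawn from the same tissue, would cover a different dose range in each patient.

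**Working it through.** The plan has no figure of its own to reproduce. Section 1.0 gives 20 evaluable subjects with no power calculation, and no section states a field size, lung volume or tumour volume. The cut-points come from 3.1 and 4.2.1. Every value of f, volume and dose distribution below is an assumption.

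Let f be the share of total lung at or above whatever dose marks the field.

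1. **Label size.** Ignoring tied doses, 'inside' is 20% of lung, 'outside' is 20%, and 60% has no label.

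2. **'Inside' tissue that is off-field.** All in-field lung lies in the top fifth when f < 0.20, so the off-field share is (0.20 − f)/0.20.
   - f = 5%: 0.15/0.20 = 75%
   - f = 10%: 0.10/0.20 = 50%
   - f = 20%: 0

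3. **Dilution.** Suppose, for illustration, that baseline uptake is even and only in-field lung changes. The mean 'inside' change is then f/0.20 of the in-field change: 25% at f = 5% and 50% at f = 10%.

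4. **Large fields.** The share of the field not labelled 'inside' is (f − 0.20)/f: 33% at f = 30%, 50% at 40%, 67% at 60%. This tissue is left out of the contrast; it is not put in the wrong region.

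5. **'Outside' tissue that is in the field.** The share is max(0, f − 0.80)/0.20. It is zero up to f = 80% and 50% at f = 90%.

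6. **Dose at the cuts.** Take in-field dose as uniform from 20 to 60 Gy and off-field dose as exponential with mean 3 + 6f Gy, capped at 20 Gy.
   - f = 5% (mean 3.3 Gy): the 80th percentile is −3.3 × ln(1 − 0.80/0.95) ≈ 6 Gy; the 20th is −3.3 × ln(1 − 0.20/0.95) ≈ 0.8 Gy.
   - f = 50% (mean 6 Gy): the 80th percentile is 20 + 40 × (0.80 − 0.50)/0.50 = 44 Gy; the 20th is −6 × ln(1 − 0.20/0.50) ≈ 3 Gy.

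   In this example the 'inside' region starts at about 6 Gy in one patient and 44 Gy in another. The 'outside' cut moves far less.

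7. **Tumour, if it is in the contour.** With normal lung V, tumour volume g, and all tumour inside the contour and above the 80th percentile, the tumour share of 'inside' is g/[0.20 × (V + g)].

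| Tumour | V = 2,500 mL | V = 4,500 mL |
|---|---|---|
| 100 mL | 100/520 = 19% | 100/920 = 11% |
| 200 mL | 200/540 = 37% | 200/940 = 21% |
| none (resected, no gross disease) | 0% | 0% |

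**The case against.** The best defence is that this is a deliberate extreme-group contrast. Hypothesis and endpoint use the same percentiles, so they agree with each other. Leaving the middle 60% unlabelled is how such contrasts work, and equal region volumes help comparison between patients. That stands for large fields: a reader might infer that leaving out much of a large field is mislabelling, but what remains in 'inside' is the highest-dose lung, and that does not dilute the contrast. It does not answer the small-field case.

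A reader might also infer that the 'outside' region is contaminated and the stability criterion therefore unsafe. The definition does not support this. 'Outside' is the lowest-dose fifth and meets the field only when the field exceeds about 80% of lung. The sole numeric criterion in 4.2.1, on stability in more than 80% of tissue, concerns that region. What remains is that its absolute dose is not reported.

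A third tempting reading is that tumour is in the analysed lung. The plan is silent on this. It speaks of lung tissue, and section 1.0 uses gradient search to find perfused and ventilated lung, which might leave tumour out. Inclusion is a possibility to close off, not an established fault.

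Finally, 4.2.2 does plot change against dose itself. This mitigates only in part, because those curves are confined to 'inside' tissue. It is also fair that dilution by off-field lung works toward no effect, so it would not by itself create a false 'inside' effect in a single-arm pilot.

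**Conclusion.** The point holds for the 'inside' label. It follows from the definition, under the natural reading that percentiles are taken within each patient's plan. The text does not say so outright, but 4.2.1 applies the cuts after fusing the images with the radiation plan. If a percentage of some maximum or prescribed dose had been meant, the label would track dose; the wording in 3.1, percentiles of total lung, argues against that.

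How much it matters depends on how many patients have a field below one fifth of lung, which the documents do not tell us. In a patient with f of 5% to 10%, between three quarters and one half of 'inside' tissue would be off-field. The tumour component is conditional on the contour and on the assumed volumes, and is nil where there is no gross disease. The change is worth making because it affects what a weak primary contrast can be taken to mean, and the plan dose is already fused to the scans.

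**What to change.** Keep the percentile contrast, and make these changes:

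- In 4.2.1, add a pre-specified co-analysis with inside and outside regions defined by absolute planned-dose levels, the same for all patients. The documents supply no value, so the team should state the levels and the reason for them before analysis.
- Report the absolute dose at each patient's 20th and 80th percentiles.
- Define total lung. Compute percentiles and uptake on one common baseline lung mask that excludes the planning gross tumour volume, applied unchanged to all three registered scans. A mask redrawn at each scan would let region membership change over time.
- In 4.2.2, fit the dose-response curves over all lung doses, not only the percentile-defined 'inside' tissue.

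No new scan or patient procedure is needed. The costs are unequal region volumes between patients in the co-analysis, some patients with little lung at a given dose level, and a little more contouring and analysis work.

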## 4.2.2 Secondary Endpoint

For the second aims (a) and (b) looking at lung tissue inside the radiation field, the images will be processed similar to primary endpoint. For lung tissue inside the radiation field, changes in tracer uptake at the global lung, regional lung, and lung image voxel scales (compared to baseline scan) will be plotted against the radiation dose at the same scales to generate multiscale radiation dose response curves. These curves will be fit to linear and sigmoid dose-response functions. We will also separate out lung regions in the upper quartile and lower quartile of ventilation and perfusion, and generate separate radiation dose response curves per region, to assess for potential differences in radiation dose response of functional lung versus non-functional lung.

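### Section 4.2.1 treats 'insignificant' out-of-field change as stability without giving a size, and no section names the outside-versus-inside estimate that the section 3.1 hypothesis needs

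*Combined protocol and SAP*

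**What the plan says.** The section 3.1 hypothesis makes two claims about lung outside the field. The first is comparative: perfusion and ventilation there "will exhibit smaller changes over time than tissue inside the radiation field". The second is directional: tissue below the 20th dose percentile "will have perfusion and ventilation that remain constant or increase at the mid-radiation treatment scan and 3-months post-treatment scans". The objective also sets out to "characterize reproducibility of perfusion and ventilation in non-irradiated lung tissue".

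Section 4.2.1 states the expected results one region at a time. Outside the field: "There should be insignificant changes in perfusion and ventilation in >80% of lung tissue outside the radiation field". Inside the field, the comparison "should yield significant differences in ventilation and perfusion between pre, mid, and post-treatment scans".

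The planned analyses are split the same way:
- **Outside (section 4.2.1):** "For lung tissue outside the radiation field, summary statistics such as total regional uptake and mean regional uptake by lobe" are to be compared across time points by unnamed parametric and non-parametric tests. Also, "Voxel-based correlation, including Pearson linear and Spearman rank, will be performed to measure the stability of uptake between time points". Dice overlap is added.
- **Inside (section 4.2.2):** "For lung tissue inside the radiation field, changes in tracer uptake at the global lung, regional lung, and lung image voxel scales" are plotted against dose and fitted to linear and sigmoid curves.
- **Synopsis (section 1.0, Statistical Methodology):** stability outside is assessed by regression, Pearson correlation and Dice; dose-response is developed inside.

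No section gives a size of change that counts as stable, a significance level, or the unit (voxel, lobe or patient) at which 'insignificant' is judged. The synopsis gives 20 evaluable subjects, without a derivation.

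**The concern.** 'Insignificant' can be read in two ways, and neither gives a usable measure of stability. Read as a test result, it rewards imprecision: the noisier the scans or the fewer the evaluable patients, the more readily tissue counts as unchanged. Read as negligible, it lacks the number that would define it. The 80% does not fill that gap, since it is a share of tissue and not a limit on how much the tissue may change.

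The comparative claim has a separate problem. One verdict for each region cannot show that one region changed less than the other. Two regions with the same true decline can fall on opposite sides of a significance threshold by chance.

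Section 2.4 gives the benefit of the study as knowing whether these scans identify lung that stays functional over time, so that it can later be protected. Followed as written, imprecise data could be reported as stability, and equal decline as a regional difference.

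**Working it through.** **No plan figure to reproduce.** The documents give no significance level, power, SD, effect size or margin behind the 20 subjects.

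**Inputs.** From the documents: n = 20 evaluable subjects, single arm, with each patient supplying both regions. Assumed: one value per patient and region, a paired t-test of change from baseline, two-sided 5%, one tracer at one follow-up scan, normal changes with equal SDs in the two regions, and between-region correlation ρ. Effects are in SDs of one region's change unless stated otherwise.

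**1. How often a real decline is 'insignificant'.** The critical value is t(0.975, 19) = 2.093, and the noncentrality is d√n.
- d = 0.30: noncentrality 0.30 × √20 = 1.34; P(not significant) = 0.753.
- The 95% CI half-width is 2.093/√20 = 0.47 SD, so a non-significant result is compatible with a considerable loss.
- Losing patients makes the result easier to obtain: at d = 0.50, P(not significant) is 0.44, 0.56 and 0.71 for n = 20, 15 and 10.

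**2. Separate verdicts when both regions decline equally.** Take a true decline of 0.45 SD in each region. P(not significant) in one region is 0.52, so P(significant) is 0.48. With independent regions, the pattern 'inside significantly down, outside not' has probability 0.48 × 0.52 = 0.25. Simulation for the correlated cases gives:

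| ρ | 'Inside down, outside not' | Direct paired contrast favours the hypothesis |
|---|---|---|
| 0.5 | 17% | about 2.5% |
| 0 | 25% | about 2.5% |
| -0.5 | 32% | about 2.5% |

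The negative case is included because section 4.2.1 does not say whether uptake is absolute or normalised to total lung. With normalised uptake, a loss in one region raises the share elsewhere.

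**3. What the other stability measures can show.** If follow-up uptake is k times baseline in every voxel (k > 0), Pearson and Spearman both equal 1 whatever the value of k. They cannot detect a uniform proportional loss. Lobe means and total uptake can detect it if uptake is absolute. If uptake is normalised to total lung, a uniform whole-lung loss is hidden from them too. None of these measures has a stated value that counts as stable.

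**4. What a direct contrast can detect at n = 20.** For 80% power at two-sided 5%, the noncentral t gives 0.66 SD of the within-patient difference. Multiplying by √(2(1−ρ)) converts this to SDs of one region's change: 0.66 × 1.00 = 0.66 at ρ = 0.5; 0.66 × 1.414 = 0.93 at ρ = 0; 0.66 × 1.732 = 1.14 at ρ = -0.5.

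**The case against.** **No inside-versus-outside information is planned at all.** A reader might infer this, but the documents do not support it. Objective 3.2(a) puts the dose-response relationship at global-lung scale among others. Section 7.1 says the baseline scan will identify functional lung both inside and outside the fields, and that dose-response curves will come from these data. A curve over the whole dose range would bear on whether low-dose lung changes less. The sections differ on scope, since section 4.2.2 and the synopsis place the curves inside the field. What stands is narrower: none of them names an outside-versus-inside contrast.

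**The sentence is a prediction, not a decision rule.** This is fair. The study is a 20-patient pilot, radiation is standard of care, and no success criterion or later step is tied to the >80% figure. That limits the consequence and argues for a light remedy, not for a formal margin test or a multi-part claim rule. It does not remove the problem, because the sentence sits in the primary endpoint and is the only statement of what stability should look like.

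**'Insignificant' may mean negligible.** This is possible. One scan per time point leaves no repeat baseline from which to estimate the noise that a tissue-level test would need. Against it, the same section plans statistical testing and expects significant differences inside. On the negligible reading, the missing size remains the defect.

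**Other stability measures are planned.** They are, so non-significance is not the sole evidence. None has a criterion.

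**Conclusion.** The concern holds in two parts: stability is expressed through 'insignificant' change with no size attached, and the comparative hypothesis has no named comparative estimate. It should be fixed before analysis, because it affects how the primary result is reported.

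The size is illustrative. At patient level with n = 20, a 0.30 SD out-of-field decline goes undetected 75% of the time. An equal 0.45 SD decline in both regions looks like a regional difference in 17-25% of trials (ρ from 0.5 to 0; about 32% at -0.5), against about 2.5% for a direct contrast. These figures rest on an assumed patient-level paired test. The documents specify neither that unit nor that test, so the figures do not evaluate the >80% tissue fraction itself.

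A reader might go further and infer that the >80% mark is shown to pass noisy scans by some stated amount. The documents cannot support a number for that: it would need repeat-scan noise, which they do not give and which one scan per time point does not measure directly. Nor does the finding show that 20 patients are too few; the plan makes no power claim.

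**What to change.** Amend section 4.2.1 before analysis:

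- **(a) Comparison.** For each tracer and follow-up scan, report each region's signed patient-level change and the paired in-field minus out-of-field difference, all with 95% CIs. Name one tracer and time point as key and the rest as supportive. Base any statement that change is smaller outside on that difference, read beside each region's own change, because a signed difference can also arise from a rise outside. Do not base it on separate significance verdicts.
- **(b) Stability.** Define 'insignificant' in the >80% measure by a size of change that the sponsor sets before analysis, and keep the fraction descriptive. Report mean out-of-field change with its CI. Make no claim of constancy from non-significance alone.
- **(c) Supporting measures.** Treat Pearson and Spearman as descriptive. State whether uptake is absolute or normalised to total lung.

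The cost is a protocol amendment and a few lines of analysis, with no new patients or scans. There are two downsides. The size band must be justified, and the documents offer no basis for one. The key contrast is also imprecise at n = 20, with 80% power only for the differences in step 4 of the working, so the pilot may end with estimates and intervals and no claim of stability or regional difference.
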